#### Modified Hematological Improvement per IWG-MDS criteria in MDS ([Cheson et al 2006](#))

HI category	Definition # (HI must last at least 8 weeks)
Erythroid response (HI-E) (pretreatment*, <math><11\text{ g/dL}</math>)	
 
1. Hgb increase from baseline by <math>\geq 1.5\text{ g/dL}</math>, in at least 2 consecutive Hgb measurements and maintained over at least 8 weeks
 
2. Relevant reduction from baseline of units of RBC transfusions by an absolute number of at least 4 RBC transfusions/8 weeks compared with the pre-treatment transfusion number in the previous 8 weeks. Only RBC transfusions given for a Hgb of <math><9\text{ g/dL}</math> pre-treatment will count in the RBC transfusion response evaluation.
 

Platelet response (HI-P) (pretreatment*, <math><100 \times 10^9/\text{L}</math>)	
 
1. Absolute increase from baseline of <math>\geq 30 \times 10^9/\text{L}</math> for participants starting with <math>>20 \times 10^9/\text{L}</math> platelets
 
2. Increase from baseline from <math><20 \times 10^9/\text{L}</math> to <math>>20 \times 10^9/\text{L}</math> and by at least
 

Neutrophil response (HI-N) (pretreatment*, <1.0 x 10^9/L)	At least 100% increase and an absolute increase from baseline of >0.5 x 10  /L
---	--

**#If not defined otherwise, all of the criteria apply. Words that are written in italics highlights the modifications from the IWG criteria described in the reference publications.**

*\*Pretreatment counts correspond to the baseline (not influenced by transfusions)*

*\*\*Definition of transfusion dependence and independence for red blood cells (RBC) and/or platelets are described below.*

*\*\*\*maximum remission/response levels correspond to the best values reported in post baseline.*

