### 8.3 Efficacy

Efficacy assessments will be performed according to the IWG and WHO criteria for MDS ([Cheson et al 2000](#), [Cheson et al 2006](#), [Arber et al 2016](#), [Platzbecker et al 2018](#)). Response criteria in MDS are described in [Table 8-2](#). Investigators will assess locally at their site and document response/progression at each time point as per the visit schedule. For efficacy analyses, baseline is defined as the last non-missing assessment on or before the date of enrollment.

The hematological improvement per modified IWG-MDS criteria ([Cheson et al 2006](#)) will be assessed in all enrolled participants to report specific hematologic improvement (HI) of cytopenias in the three hematopoietic lineages: erythroid (HI-E), platelet (HI-P), and neutrophil (HI-N).

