| Platelet response (HI-P) (pretreatment*, $<100 \times 10^9/L$) | 
 1. Absolute increase from baseline of $\geq 30 \times 10^9/L$ for subjects starting with $>20 \times 10^9/L$ platelets 2. Increase from baseline from $<20 \times 10^9/L$ to $>20 \times 10^9/L$ and by at least 100% for subjects starting with $<20 \times 10^9/L$ platelets |
| Neutrophil response (HI-N) (pretreatment*, $<1.0 \times 10^9/L$) | At least 100% increase and an absolute increase from baseline of $>0.5 \times 10^9/L$ |

#If not defined otherwise, all of the criteria apply. Words that are written in *italics* highlights the modifications from the IWG criteria described in the reference publications.

**Pretreatment counts correspond to the baseline (not influenced by transfusions)*

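### As written, erythroid improvement (HI-E) needs both a hemoglobin rise and a drop of at least 4 RBC transfusions, so anemic participants with fewer than 4 counted baseline units can never respond

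*Protocol*

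**What the plan says.** Protocol 8.3 commits to HI reporting by lineage. HI "will be assessed in all enrolled participants to report specific hematologic improvement (HI) of cytopenias in the three hematopoietic lineages": erythroid, platelet and neutrophil. The definitions stand in the HI part of Protocol Table 8-2 and are copied into SAP Table 2-6 (Section 2.7.1).

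The definition column carries footnote #, which reads "If not defined otherwise, all of the criteria apply". The HI-E row is open to participants with pre-treatment hemoglobin below 11 g/dL and lists two numbered criteria with no connecting word:

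- Criterion 1 is a hemoglobin rise of at least 1.5 g/dL, "in at least 2 consecutive Hgb measurements and maintained over at least 8 weeks".
- Criterion 2 reads "Relevant reduction from baseline of units of RBC transfusions by an absolute number of at least 4 RBC transfusions/8 weeks", set against the 8 weeks before treatment. Only transfusions given for a hemoglobin below 9 g/dL count.

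In the same table, the relapse and progression rows each say that meeting any one listed item is enough. The HI rows contain no such statement.

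The platelet row (HI-P) also has two criteria. The first is limited by the words "for participants starting with" to counts above 20 x10^9/L. The second, complete in the SAP, requires an increase to above 20 "and by at least 100% for subjects starting with" less than 20.

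**The concern.** A footnote that makes listed criteria cumulative unless a row says otherwise is a rule, and the HI-E row does not depart from it. The row admits anyone with hemoglobin below 11 g/dL, yet its second criterion can be met only by someone with a substantial baseline transfusion load. The two conditions together give a response category that part of its own target population cannot reach.

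What is at stake is classification. Protocol 8.3 leaves response assessment to investigators at their sites, and SAP 2.7.1 says the category definitions captured in the eCRF are those of this table. A site or programmer following the text would score as a non-responder a participant whose hemoglobin rose by well over 1.5 g/dL for 8 weeks. One who assumed an either/or rule would score the same participant as a responder. The documents do not say which applies beyond the footnote, and the footnote points to the first.

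**Working it through.** The documents state no HI rate, sample size or precision figure, so there is no figure to reproduce. The check is one of logic.

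**Inputs.** The default combination rule is footnote # in both tables. The HI-E entry condition is hemoglobin below 11 g/dL. Criterion 2 requires a drop of at least 4 transfusions per 8 weeks, counting only those given for hemoglobin below 9 g/dL. Baseline transfusion dependence is at least 3 units in the 8 weeks before baseline (transfusion status definitions, Protocol 8.3). The row uses both units and transfusions; I take one unit as one transfusion.

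**HI-E.** Let b be the counted RBC units in the 8 weeks before treatment. The post-treatment count cannot fall below 0, so the largest possible drop is b - 0 = b. Criterion 2 is reachable only if b >= 4.

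| b | Largest drop | Criterion 2 reachable | Transfusion dependent at baseline |
|---|---|---|---|
| 0 | 0 | no | no |
| 1 | 1 | no | no |
| 2 | 2 | no | no |
| 3 | 3 | no | yes |
| 4 | 4 | yes | yes |

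If both criteria are required, HI-E is closed for b = 0, 1, 2 or 3 whatever the hemoglobin does. This includes the participant at exactly 3 units, whom the protocol itself calls transfusion dependent. If either criterion suffices, all of these participants can respond through the hemoglobin rise.

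**Size.** Let s be the share of participants with hemoglobin below 11 g/dL who have at least 4 counted units. Under the cumulative rule the HI-E rate in that group cannot exceed s, and 1 - s are non-responders by definition. The documents do not give s. Purely as assumptions, s = 30%, 50% or 70% would put 70%, 50% or 30% beyond reach.

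**HI-P.** The two starting ranges, above 20 and below 20, do not overlap. With each criterion applied to its own group, 99 of the 100 integer starting counts from 0 to 99 have a usable criterion. The exception is a count of exactly 20, which falls in neither group.

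**Evidence on intent.** Protocol 6.1.4.1, on treatment beyond progression, sets improved or stable cytopenia and reduced transfusion need as alternatives, either of which is enough. That is the same pair of ideas as the two HI-E criteria, which suggests that the missing either/or in the HI-E row is a drafting gap.

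**The case against.** The strongest reply is that the HI-E row is ambiguous and does not settle on the cumulative rule. Criterion 2 limits which transfusions given "pre-treatment will count in the RBC transfusion response evaluation", and that phrase suggests a transfusion route separate from the hemoglobin route. The table is also headed as following the IWG-MDS criteria, with italics marking departures, and italics cannot be seen in extracted text. This supports either/or as the intended meaning. It does not change what the footnote says, and nothing in the HI-E row displaces it. An argument about intent is a reason to correct the row.

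A second reply is that nothing visible depends on HI. This stands. HI is not among the eight secondary endpoints, SAP best overall response has no HI category, and no unredacted SAP section derives or tabulates it. Any use in redacted text cannot be assessed.

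Two stronger readings are tempting and should not be drawn. A reader might infer that the cumulative rule forces the platelet response rate to zero, because nobody can start both above and below 20. But each platelet criterion names its own baseline group, which is fairly read as a case defined otherwise, so each participant is judged on the one that fits. Only the gap at exactly 20 remains. A reader might also infer that HI rates here could not be set beside the stable disease with hematologic improvement reported for the phase Ib study in Protocol 4.3.2. The documents do not give the HI rule used in that study, and this trial is descriptive with no such comparison planned.

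**Conclusion.** The point holds for HI-E. Under the footnote as written, any participant with hemoglobin below 11 g/dL and fewer than 4 counted pre-treatment RBC units is excluded from erythroid response by arithmetic, including one who is transfusion dependent at 3 units. This is a stated rule that misclassifies, and it sits badly with the promise to assess HI in everyone enrolled.

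The consequence is limited to the HI-E rate in Protocol 8.3. CR and the other response rates, PFS, OS, LFS, duration of and time to CR, and transfusion independence do not use it. The size in this trial is unknown because the baseline transfusion distribution is not given; the shares above are assumptions. The conclusion rests on the footnote governing the HI-E row, which the column marking supports, and on counting one unit as one transfusion. The platelet row needs clarification only.

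**What to change.** In the HI-E row of Protocol Table 8-2 and SAP Table 2-6, state that meeting either criterion is enough, using the same kind of override as the relapse and progression rows. Add a note that criterion 2 can be met only by participants with at least 4 counted RBC units in the 8 weeks before treatment. As a minor clarification in the HI-P row, say that the criteria apply by baseline platelet group and assign a starting count of exactly 20 x10^9/L to one of them. The documents do not favor either side, so the sponsor should choose and record it.

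The wording costs about one phrase per row. The SAP document history places Addendum 02 after database lock, so the SAP change should be a dated, documented clarification, and any reported HI-E rate should state which rule was used. The hemoglobin criterion can be re-derived from the hematology data. Criterion 2 is less certain: Protocol 6.2.1 and 8.2 require transfusions to be recorded from 16 weeks before enrollment, but neither says that the hemoglobin prompting each transfusion is recorded. That should be checked first, because without it the restriction to transfusions given below 9 g/dL cannot be applied.

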#### **Transfusions Status Definitions for RBC/platelets**

**Transfusions for intercurrent diseases not due to MDS (e.g. bleeding, surgical procedure, hemolysis, infections) should not be taken into account for the following:**

##### **Transfusion dependence:**

1. At baseline: participants having received  $\geq$  3 units of transfusion within the 8 consecutive weeks prior to baseline.
2. Post-baseline: participants having received  $\geq$  3 units of transfusion within any 8 consecutive weeks during the course of the study

More frequent efficacy assessments may be performed at the investigator's discretion, if medically indicated, and recorded as an unscheduled visit in the eCRFs.

## **Extension phase**

Patients completing core phase of 12 months and requiring continuation of study treatment (by investigator decision) beyond 12 months will enter the extension phase. For patients that will receive treatment in the extension phase, they are allowed to continue treatment with MBG453 and azacitidine/decitibine/INQOVI (oral decitibine), azacitidine/decitibine/INQOVI (oral decitibine) alone, or MBG453 alone.

Additionally, for participants who discontinue any study treatment for reasons other than documented disease progression, death, lost to follow-up, or withdrawal of consent, will enter extension phase.

Efficacy assessments (hematology and bone marrow aspirate/biopsy) should follow [Table 8-1](#). Response assessments must continue to be performed every 3 cycles as per hematology assessment and at least every 6 cycles as per bone marrow assessment or as clinically indicated until documented disease progression/relapse (per IWG criteria [Table 8-2](#)), death, lost to follow-up, or withdrawal of consent.

### **8.3.1      Appropriateness of efficacy assessments**

Not applicable.

## **8.4      Safety**

Safety assessments are specified below [Table 8-3](#) with the assessment schedule detailing when each assessment is to be performed.

For safety evaluations, baseline is defined as assessments done on C1D1 prior to the first dose of study treatment. For assessment which are not done at C1D1 as per [Table 8-1](#), baseline is defined as the last available assessment prior to C1D1.

The investigator will report any vital signs considered clinically significant in the eCRF. For details on AE collection and reporting, refer to AE [Section 10.1.1](#).

As per section 4.6, during a Public Health emergency as declared by Local or Regional authorities i.e. pandemic, epidemic or natural disaster, that limits or prevents on-site study visits, regular phone or virtual calls can occur (every Y weeks or more frequently if needed) for safety monitoring and discussion of the participant's health status until it is safe for the participant to visit the site again.

If participants cannot visit the site to have serum pregnancy tests, urine pregnancy test kits may be used. Relevant participants can perform the urine pregnancy test at home and report the result to the site. It is important that participants are instructed to perform the urine pregnancy test first and only if the test result is negative proceed with the administration of the study treatment.

A communication process should be established with the participant so that the Site is informed and can verify the pregnancy test results (e.g. following Country specific measures).

If participants cannot visit the site for protocol specified safety lab assessments, an alternative lab (local) collection site may be used.

**Table 8-3 Assessments & Specifications**

Assessment	Specification
Physical examination	A complete physical examination will include the examination of general appearance, skin, neck (including thyroid), eyes, ears, nose, throat, lungs, heart, abdomen, back, lymph nodes, extremities, vascular and neurological. Information for all physical examinations must be included in the source documentation at the study site. Clinically relevant findings that are present prior to signing informed consent must be recorded on the appropriate CRF that captures medical history. Significant findings made after signing informed consent which meet the definition of an Adverse Event must be recorded as an adverse event.
Vital signs	Vital signs include blood pressure (supine position preferred when ECG is collected), pulse measurement and body temperature.
Height and weight	Height will be measured at screening. Body weight (in indoor clothing, but without shoes) will be measured and BSA will be calculated as specified in Table 8-1 .

### **Performance status:**

ECOG Performance status scale will be used as described in [Table 8-4](#) and collected as specified in [Table 8-1](#).

**Table 8-4 ECOG performance status**

Grade	ECOG Status
0	Fully active, able to carry on all pre-disease performance without restriction
1	Restricted in physically strenuous activity but ambulatory and able to carry out work of a light or sedentary nature (e.g., light house work, office work)
2	Ambulatory and capable of all self-care but unable to carry out any work activities. Up and about more than 50% of waking hours
3	Capable of only limited self-care, confined to bed or chair more than 50% of waking hours
4	Completely disabled. Cannot carry on any self-care. Totally confined to bed or chair
5	Death

#### **8.4.1 Laboratory evaluations**

Local clinical laboratory parameters will be used for the analysis of scheduled hematology, chemistry and other blood specimens collected as part of safety monitoring (as detailed in [Table 8-1](#) and [Table 8-5](#)) and the results will be collected in the eCRF.

Unscheduled assessments of these parameters can be performed more often as clinically indicated. It is preferable to use the same laboratory for all the assessments performed, especially for hematology.

Laboratory values obtained during the Screening phase will be used to assess participant's eligibility.

Novartis must be provided with a copy of the certification and a tabulation of the normal ranges and units for all local laboratories used to in the trial.

Clinically significant abnormalities must be recorded as either medical history/current medical conditions or adverse events as appropriate.

There are no specific notable range criteria for this study; however, the local laboratory will flag laboratory values falling outside of the normal range, on the local report (as applicable) (which the investigator should sign off) as per local practice, and the investigator will report any values considered clinically significant in the eCRF.

**Table 8-5 Local clinical laboratory parameters collection plan**

Test Category	Test Name
Hematology	Hematocrit, Hemoglobin, MCH, MCHC, MCV, Platelets, Red blood cells, White blood cells, RBC Morphology, Differential (Basophils, Eosinophils, Lymphocytes, Monocytes, Neutrophils, Bands), Blasts, Other (absolute value preferred, %s are acceptable)
Chemistry	Albumin, Alkaline phosphatase, ALT, AST, Gamma-glutamyl-transferase (GGT), Lactate dehydrogenase (LDH), Calcium, Magnesium, Phosphorus, Sodium, Potassium, Creatinine, Creatine kinase, Direct Bilirubin, Indirect Bilirubin, Total Bilirubin, Total Cholesterol, Total Protein, Blood Urea Nitrogen (BUN) or Urea, Uric Acid, Amylase, Lipase, Glucose (fasting), Troponin T
Virology*	HBsAg, HBcAb, HBV DNA (in participants positive for HBcAb), HCV RNA (PCR) HIV (Only if required by local regulation)
Coagulation	International normalized ratio (INR), Activated partial thromboplastin time (aPTT)
Cytokines***	IFN- $\gamma$ , IL-6, IL-1, TNF- $\alpha$
Urinalysis dipstick and sediment*	Dipstick examination includes specific gravity, pH, glucose, protein, blood, bilirubin, ketones and WBC as clinically indicated
Pregnancy Test*	Serum / Urine pregnancy test (refer to 'Pregnancy and assessments of fertility' section)

\*Virology, urinalysis and pregnancy test will only be reported in the source documentation.

\*\*Preferred method is erythrocyte folate but in case is not available then serum should be performed. However, every effort should be made to perform both test.

#### 8.4.2 Electrocardiogram (ECG)

Three sequential (triplicate) 12 lead ECGs are to be collected with ECG machines available at the site at Screening and at End of Treatment. Additional, unscheduled, safety ECGs may be repeated at the discretion of the investigator at any time during the study as clinically indicated (Table 8-6). Unscheduled ECGs with clinically significant findings should be collected in triplicate. Interpretation of the tracing must be made by a qualified physician and documented in the source documents at site. Each ECG tracing should be labeled with the study number, subject initials (where regulations permit), date, and kept in the source documents at the study site. Local cardiologist ECG assessment may also be performed at any time during the study at the discretion of the investigator. Clinically significant abnormalities present at screening should be reported on the appropriate CRF. Clinically significant findings must be discussed with Novartis prior to enrolling the patient in the study. New or worsened clinically significant findings occurring after informed consent must be recorded as adverse events.

Electrocardiograms (ECGs) must be recorded after 10 minutes rest in the supine position to ensure a stable baseline. The individual ECGs should be recorded approximately 3 minutes apart. The preferred sequence of cardiovascular data collection during study visits is ECG collection first, followed by vital signs, and blood sampling. The Fridericia QT correction formula (QTcF) should be used for clinical decisions.

For any ECGs performed in a subject for safety concerns, two additional ECGs must be performed to confirm the safety finding.

Clinically significant abnormalities (including clinically significant ECG findings) must be recorded on the CRF as either medical history/current medical conditions or adverse events as appropriate. Follow-up in case of QT prolongation should be performed as per Section 6.5.1.2.

**Table 8-6 Local ECG collection plan**

Visit	Day	Time	ECG Type
Screening	-28 to -1	Anytime	12 Lead
End of Treatment	-	Anytime	12 Lead
Unscheduled or Unplanned sample	-	Anytime	12 Lead

### **8.4.3 Pregnancy and assessments of fertility**

#### **Female patients**

All pre-menopausal women who are not surgically sterile will have pregnancy testing. Additional pregnancy testing might be performed if requested by local requirements.

At screening, a serum pregnancy test (serum  $\beta$ -HCG) must be performed within 72 hours before the first dose of study treatment.

During the study, a urine/serum pregnancy test should be done locally at Day 1 of each cycle (except if for Cycle 1 a pregnancy test was performed within 72 hours of the first dose) and at EOT visit. Additionally, during the post treatment safety follow up, women of child bearing potential will be tested monthly with urine or serum pregnancy tests up to Day 90 after the last dose of azacitidine or decitabine or INQOVI (oral decitabine). They will also be tested monthly with urine or serum pregnancy tests up to Day 150 after the last dose of MBG453 (sabatolimab), and a serum pregnancy test should be performed on Day 150 after the last dose of MBG453 (sabatolimab). If the participant is not coming to the clinic during the safety follow-up period, the test can be performed at home or at a local doctor's office, and the results will be communicated to the site staff.

A positive urine pregnancy needs to be confirmed with a serum test. Confirmed positive pregnancy test requires immediate discontinuation of study treatment and discontinuation from study see [Section 10.1.4](#) for pregnancy reporting.

The pregnancy tests will be recorded only in the source documentation, not in the CRF.

Women of childbearing potential should employ the use of highly effective contraception during study treatment, for 3 months after the last dose of azacitidine or decitabine or INQOVI (oral decitabine) (or as per their respective local labels, whichever is longer) and 150 days after the last dose of MBG453 (sabatolimab). Highly effective contraception methods are defined in [Section 5.2](#).

Medical documentation of oophorectomy, hysterectomy, or tubal ligation must be retained as source documents. Subsequent hormone level assessment to confirm the woman is not of child-bearing potential must also be available as source documentation in the following cases:

1. Surgical bilateral oophorectomy without a hysterectomy
2. Reported 12 months of natural (spontaneous) amenorrhea with an appropriate clinical profile.

In the absence of the above medical documentation, FSH testing is required of any female participant regardless of reported reproductive/menopausal status at screening/baseline.

